8.4.2. Pharmacokinetic Analysis

The data will be analyzed by standard population PK methods using appropriate software (eg, NONMEM®). An attempt will be made to evaluate the effect of demographic and baseline characteristics (eg, age, weight, sex, race, renal function, and FGF/FGFR alteration status) on the population PK profile. Additionally, exposure-response analyses for key efficacy and safety parameters will also be considered if there are sufficient data available.

8.5. Pharmacodynamic and Translational Assessments

8.5.1. Biomarker Assessment for Eligibility

Participants will be required to have a documented actionable FGFR1-3 gene alteration (including defined mutations, gene fusion/rearrangements, or in-frame deletions; see [Appendix B](#)) from tumor tissue (or plasma) as determined by a locally qualified laboratory employing a molecular assay having a relevant mark of conformity for analytical performance (eg, CLIA [US] or UKCA, CE, CE UKNI, or others [outside of the US]) or a commercial report from the central laboratory to be eligible. [Appendix B](#) contains a list of eligible gene alterations and known FGFR resistance mutations. [Appendix B](#) is not all-inclusive, so extremely rare or novel activating alterations may not be in the list.

Participants may be enrolled and can receive treatment based on a local genomics report (non-FMI and commercial FMI reports) or from the central genomics laboratory (FMI). For participants enrolled based on a local genomics report for tumor tissue or blood cfDNA (Guardant Health or commercial FMI for liquid biopsies), they will be required to provide a redacted genomics laboratory result documenting the eligible alteration for sponsor review after signing the ICF. Additionally, for participants enrolled with a local genomic report, tumor tissue sample (either archival or fresh biopsy) should be sent to the sponsor's central genomics laboratory (FMI) for retrospective confirmation of eligible FGFR1-3 gene alterations (results from central review are not required before the first dose).

Archival tissue, or fresh biopsy if archival tissue is not available, is expected at screening for confirmation testing of FGFR1-3 mutation or rearrangement at central genomic laboratory using F1CDx assay. Participants who have a commercial report from the central laboratory (FMI) at screening will not need to send a sample for confirmatory testing. Details regarding sample collection, processing, and shipping will be provided in the Laboratory Manual.

In addition to confirmation of the FGFR alteration, baseline tumor tissue may be used for IHC, gene-expression profiling, tumor mutation burden, and immune-cell profiling in order to study

baseline characteristics of the tumor and tumor microenvironment for potential correlations with response, resistance, or toxicity to pemigatinib.

8.5.2. Plasma for Mutational Analysis

Blood for mutational analysis of cfDNA will be collected predose on Cycle 1 Day 1 (baseline) and at disease progression or EOT (see [Table 4](#) and [Table 14](#)). Analysis of tumor mutational status will be conducted by the sponsor or its designee, and other assays relevant to the objectives of the study may be performed based upon emerging data. Details regarding sample collection, processing, and shipping will be provided in the Laboratory Manual.

8.5.3. Plasma for Correlative Analysis

Blood for plasma biomarker analysis will be drawn for all participants at predose on Cycle 1 Day 1 and any time on Cycle 1 Day 8 and Cycle 4 Day 1 (see [Table 4](#) and [Table 14](#)). Additional assessments may be collected in order to correlate potential biomarkers with AEs, response, or resistance to treatment. The analyses may include assessment of markers of immune and inflammation status, including cytokines and soluble receptors, as well as examination of markers associated with tumor metabolism. Other assays relevant to the objectives of the study may be performed based upon emerging data. Details regarding sample collection, processing, and shipping will be provided in the Laboratory Manual.

8.5.4. Tissue Biopsies

Tumor biopsies will be collected at the timepoints indicated in [Table 4](#) and [Table 14](#) as follows:

- **Screening:** Tumor tissue may be collected during screening. Archival formalin-fixed paraffin-embedded tissue sample is expected or a fresh biopsy may be performed if archival tissue is not available.

Note: Fresh tumor biopsies should be taken from nontarget lesions when possible.

- **End of Treatment:** A biopsy at EOT/the time of progression is requested but not required from all participants. Analysis of the tumor tissue will assist in understanding the changes that occur in genomic alterations after treatment with pemigatinib. If EOT occurs less than 6 weeks after the on-treatment biopsy was performed, an EOT biopsy should not be performed.

Table 14: Biomarker/Translational Sample Timing

| Biomarker Assessment | Study Visit | Timing of Sample | |
|-----------------------------|--------------------|-------------------------|----------------|
| | | Anytime | Predose |
| Plasma correlative sample | Cycle 1 Day 1 | | X |
| | Cycle 1 Day 8 | X | |
| | Cycle 4 Day 1 | X | |
| Plasma cfDNA | Cycle 1 Day 1 | | X |
| | EOT | X | |
| Tumor tissue | Screening | X | |
| | EOT | X | |

8.6. Unscheduled Visits

Unscheduled visits may occur as clinically indicated. They can be used for visits that occur outside of visit windows and should be noted in the eCRF as an unscheduled visit.

8.7. End of Treatment and/or Early Termination

When the participant permanently discontinues study drug whether the participant is terminating the study early or the participant has completed the study, the EOT visit should be conducted. If the EOT visit coincides with a regular study visit, the EOT evaluations will supersede those of that scheduled visit, and the data should be entered in the EOT visit in the eCRF. The participant should be encouraged to return for the follow-up visit.

8.8. Follow-Up

8.8.1. Safety Follow-Up

The safety follow-up period is the interval between the EOT visit and the scheduled follow-up visit, which should occur 30 days after the EOT visit (or after the last dose of study drug if the EOT visit was not performed). Adverse events and SAEs must be reported up until 1) at least 30 days after the last dose of study drug or the start of a new anticancer therapy or 2) until toxicities resolve, return to baseline, or are deemed irreversible, whichever is longer. Reasonable efforts should be made to have the participant return for the follow-up visit and report any AEs that may occur during this period. If the participant cannot return to the site for the safety follow-up visit (eg, lives far away), the participant should be contacted by telephone for assessment of AEs and SAEs. Sites should be instructed to document this contact in the source.

If a participant is scheduled to begin a new anticancer therapy before the end of the 30-day safety follow-up period, the safety follow-up visit should be performed before the new anticancer therapy is started. Once a new anticancer therapy has been initiated, the participant will move into the survival follow-up period.

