4.2. Overall Study Duration

The study begins when the first participant signs the study ICF.

The study will include up to 28 days for screening, 2 weeks on and 1 week off treatment in consecutive 21-day cycles as long as participants are receiving benefit and have not met any criteria for study withdrawal, and 28 (must be a minimum of 28 days) to 30 days for follow-up after the last dose of study drug. It is estimated that an individual will participate for approximately 3 months.

A participant is considered to have completed the study if he/she has completed all parts of the study including the last visit. A study is considered completed when the last participant last visit has occurred.

If there have been ≤ 3 participants on study for more than 6 months, a database lock of the study may occur, and the study may be considered completed to allow the analysis of the study data. Any remaining participants may continue to receive study treatment and be seen by the investigator per usual standard of care for this population. The investigator will be expected to monitor for and report any SAEs, and pregnancies as detailed in Section [9](#). The remaining participants are considered to be on study until a discontinuation criterion is met.

The end of the study will occur when all participants have been followed for at least 1 year after the initiation of study treatment, death, or withdrawal of consent, whichever occurs first.

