8.3.1. Adverse Events

Adverse events will be monitored from the time the participant signs the ICF until at least 30 days after the last dose of study drug or until the start of new anticancer therapy. Adverse events for enrolled participants that begin or worsen after informed consent should be recorded on the Adverse Events Form in the eCRF regardless of the assumption of a causal relationship with the study drug. Conditions that were already present at the time of informed consent should be recorded on the Medical History Form in the eCRF. Adverse events (including laboratory abnormalities that constitute AEs) should be described using a diagnosis whenever possible rather than by individual underlying signs and symptoms.

Adverse events will be reported by the participant (or, when appropriate, by a caregiver, surrogate, or the participant's legally authorized representative). The investigator and any qualified designees are responsible for detecting, documenting, and recording events that meet the definition of an AE or SAE and remain responsible for following-up on AEs that are serious, considered related to the study drug/procedures, or that caused the participant to discontinue the study drug. Care will be taken not to introduce bias when detecting AEs and/or SAEs.

Open-ended and nonleading verbal questioning of the participant, such as "How are you feeling?" is the preferred method to inquire about AE occurrences. Adverse events may also be detected when they are volunteered by the participant during the screening process or between visits or through physical examinations, laboratory tests, or other assessments. The definition, reporting, and recording requirements for AEs are described in Section [9](#).

All SAEs will be reported to the sponsor or designee within 24 hours. The investigator will submit any updated SAE data to the sponsor within 24 hours of it being available.

After the initial AE/SAE report, the investigator is required to proactively follow each participant at subsequent visits/contacts. All SAEs will be followed until resolution, stabilization, the event is otherwise explained, or the participant is lost to follow-up (as defined in Section [7.3](#)).

For Japan, the relationship of the adverse event to phosphate binder(s) should also be collected on the Adverse Events Form in the eCRF.

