9.4. Reporting of Serious Adverse Events

Regardless of suspected causality (eg, relationship to study drug or study procedure[s]), all SAEs occurring after the participant has signed the ICF through 30 days after the last dose of study drug *or* until the participant starts a new anticancer therapy, whichever occurs earlier, must be reported to the sponsor (or designee) immediately, without undue delay but not later than within **24 hours** of obtaining knowledge of its occurrence unless otherwise specified by the Protocol. The investigator will submit any updated SAE data to the sponsor (or designee) immediately, without undue delay but not later than within 24 hours of it being available. For Japan, this information must also be reported immediately to the head of the study site.

Investigators are not obligated to actively seek SAE information after 30 days after the last dose of study drug. If the investigator learns of any SAE, including death, at any time during the survival period and he/she considers the event to be reasonably related to the study drug or study participation, then the investigator must notify the sponsor (or designee) within 24 hours of becoming aware of the event.

After the initial AE/SAE report, the investigator is required to proactively follow each participant at subsequent visits/contacts. All SAEs will be followed until resolution, stabilization, the event is otherwise explained, or the participant is lost to follow-up (as defined in Section 7.3).

Prompt notification by the investigator to the sponsor regarding an SAE is essential so that legal obligations and ethical responsibilities toward the safety of participants and the safety of a study drug under clinical investigation are met.

If the SAE is not documented in the RSI of the **IB** for the study drug (new occurrence) and is thought to be related to the study drug, the sponsor or its designee may urgently require further

information from the investigator for expedited reporting to health authorities. The sponsor or its designee may need to issue an Investigator Notification to inform all investigators involved in any study with the same drug that this SAE has been reported. Suspected unexpected serious adverse reactions will be collected and reported to the competent authorities and relevant ethics committees in accordance with Directive 2001/20/EC or as per national regulatory requirements in participating countries.

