8.2. Adverse Events

8.2.1. Adverse Event Definitions

A TEAE is any AE either reported for the first time or worsening of a pre-existing event after the first dose of study drug until 30 days after the last dose of study drug. Analysis of AEs (as discussed below) will be limited to TEAEs, but data listings will include all AEs regardless of their timing in relation to study drug administration. For purposes of analysis, all AEs will be considered TEAEs unless the AE can unequivocally be defined as not treatment-emergent.

Adverse events will be tabulated by MedDRA PT and SOC. Severity of AEs will be graded using the NCI CTCAE v5.0. The CTCAE reporting guidelines and grading details are available on the Cancer Therapy Evaluation Program website.

A grading (severity) scale is provided for each AE term. If the toxicity is not included in the CTCAE v5.0 criteria, it will be graded on a scale of 1 to 5 as follows: 1 = mild, 2 = moderate, 3 = severe, 4 = life-threatening, and 5 = fatal. All toxicities will be graded based on the worst level reached, not the level they may have reached if they had not been treated. When the intensity of an AE changes over time for a reporting period (eg, between visits), each change in intensity will be reported as an AE until the event resolves.

The subset of AEs considered by the investigator to be related to study drug will be considered to be treatment-related AEs. If the investigator does not specify the relationship of the AE to study drug, the AE will be considered to be treatment-related. The incidence of AEs and treatment-related AEs will be tabulated. In addition, serious TEAEs will also be tabulated.

Any missing onset date, causality, or severity must be queried for resolution. Unresolved missing causality and severity will be handled according to the following rules:

- An unresolved missing causality will be considered treatment-related.
- An unresolved missing severity will be identified as an unknown severity.

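### Protocol 8.8.1 and 9.4 set conflicting end points for SAE reporting when a participant switches therapy with an unresolved toxicity, and the 30-day TEAE window does not match the 9.4 collection window for anyone who switches early

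*Protocol*

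**What the plan says.** **Collection and reporting.** Protocol 9.4 requires all SAEs, whatever their cause, to be reported through 30 days after the last dose or "until the participant starts a new anticancer therapy, whichever occurs earlier". After that, an SAE the investigator learns of is reportable only if considered reasonably related to the drug or to study participation. The same section states that "Investigators are not obligated to actively seek SAE information after 30 days after the last dose of study drug".

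Protocol 8.8.1 sets two limits. The first is worded "Adverse events and SAEs must be reported up until 1) at least 30 days after the last dose of study drug", with the start of a new anticancer therapy given as an alternative. The second runs "until toxicities resolve, return to baseline, or are deemed irreversible, whichever is longer". The section also asks for the safety visit to take place before a new therapy begins, and adds: "Once a new anticancer therapy has been initiated, the participant will move into the survival follow-up period".

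Protocol 8.3.1 monitors adverse events (AEs) from consent "until at least 30 days after the last dose of study drug or until the start of new anticancer therapy". Protocol 7.1.2 has participants who stop treatment followed for safety to the later of the follow-up visit and resolution of drug-related toxicity, and does not mention new therapy.

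**Analysis.** SAP 8.2.1 defines a treatment-emergent adverse event (TEAE) as one that is new or worsens "after the first dose of study drug until 30 days after the last dose of study drug". Protocol 10.4.3 uses the same 30 days. Neither cuts the window at new therapy.

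**Visit timing.** Protocol 4.2 provides for "28 (must be a minimum of 28 days) to 30 days for follow-up after the last dose of study drug", and Table 2 gives 30 days after the last dose. Section 8.8.1 and Table 3 place the safety visit 30 days after the end-of-treatment (EOT) visit; 8.8.1 falls back on the last dose if no EOT visit took place.

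**The concern.** A site cannot follow both 8.8.1 and 9.4 for a participant who begins another therapy while a toxicity is unresolved. One section requires SAE reporting to continue; the other ends it, apart from related events. SAE reporting carries a 24-hour obligation, so sites need one unambiguous end point.

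The second issue is the match between what is collected and what is tabulated. SAP 8.2.3 reports TEAEs as plain numbers and percentages of participants. If collection stops at the switch, the participant stays in the denominator as though watched for the full 30 days. If collection continues, events arising under the next regimen fall inside the pemigatinib TEAE window with nothing to mark them. Two SAP 8.2.1 conventions add to this: an AE counts as treatment-emergent unless it clearly is not, and a causality still missing after query is set to related.

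Safety and tolerability is a secondary objective. Expected participation is about 3 months, so a 30-day tail is roughly a third of that length.

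**Working it through.** The plan gives no figure to reproduce. The check sets the rules side by side and applies them to one timeline.

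**Inputs.** Rules come from Protocol 7.1.2, 8.3.1, 8.8.1, 9.4 and 10.4.3 and SAP 8.2.1. Assumed dates, counted from the last dose as day 0: new anticancer therapy on day 10; an existing toxicity that resolves on day 45; a new SAE, judged unrelated, on day 20.

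| Rule | Covers | End point in this example | Day-20 unrelated SAE |
|---|---|---|---|
| Protocol 9.4 | SAEs | earlier of 30 and 10 = day 10 | not required |
| Protocol 8.3.1 | AEs | day 10, or day 30 or later; no ranking given | unclear |
| Protocol 8.8.1 | AEs and SAEs | later of limit 1 (day 10, or day 30 or later) and limit 2 (day 45); day 45 if limit 1 ends by then | required |
| Protocol 10.4.3, SAP 8.2.1 | TEAE tables | day 30 | counts as a TEAE if recorded |

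**Step 1: the explicit clash.** With the toxicity unresolved, 8.8.1 runs to day 45 and 9.4 to day 10. The same SAE is mandatory under one and not required under the other.

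**Step 2: remove the unresolved toxicity.** Limit 2 of 8.8.1 then adds nothing. Limit 1 remains, and it carries the same unranked alternative as 8.3.1. The text is ambiguous, but it no longer plainly contradicts 9.4.

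**Step 3: collection against analysis.** This mismatch needs no unresolved toxicity. For a switch on day s, with s no greater than 30, the TEAE window has 30 − s days beyond the routine SAE period of 9.4. At s = 10 that is 30 − 10 = 20 days. The gap cannot exceed 30 days per participant and is zero for anyone who does not switch within 30 days. Events after day 30 are outside the TEAE tables in any case.

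**Step 4: section 9.4 itself.** Saying that active seeking is not obligatory after day 30 implies that it is expected up to day 30. The reporting rule in the same section can end sooner.

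**Step 5: the visit anchor.** Illustration on 21-day cycles, assuming the last dose on Cycle 3 Day 14 and EOT on Cycle 4 Day 1:

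- last dose: 2 × 21 + 14 = study Day 56
- EOT: 3 × 21 + 1 = Day 64
- safety visit under 8.8.1 and Table 3: 64 + 30 = Day 94, which is 94 − 56 = 38 days after the last dose
- period under 4.2: 56 + 28 = Day 84 to 56 + 30 = Day 86
- TEAE window closes: 56 + 30 = Day 86

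The anchors differ, but the Day 94 visit can still ask about the whole window. The earliest date allowed by 4.2, Day 84, falls 86 − 84 = 2 days before the window closes.

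**The case against.** The strongest reply is that this is a small drafting discrepancy and that 8.8.1 already deals with early switchers. It asks for the safety visit before the switch and then moves the participant to survival follow-up, which points the same way as 9.4. Its second limit can be read as follow-up of toxicities already recorded, as in 7.1.2 and 9.3, and not as collection of new events. Related SAEs remain reportable under 9.4 throughout survival follow-up. TEAEs are defined by timing, not cause, and SAP 8.2.3 has separate tables for treatment-related events.

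Much of this stands, and it limits the consequence. It does not remove the contradiction: 8.8.1 says that AEs and SAEs must be reported, not merely followed. Nor does a visit before the switch recover unrelated events that begin after it.

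Three stronger readings are tempting and lack support:

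- A reader might infer that 8.3.1 shares the earlier-of rule. Only 9.4 states one, and only for SAEs.
- A reader might infer that 8.8.1 secures all 30 days for any participant switching on day 10, so that two-thirds of the window turns on the section a site follows. Limit 1 of 8.8.1 itself names new therapy, so a definite extension beyond it needs an unresolved toxicity. The 20 days in the working compare 9.4 with the TEAE window, which is a different comparison.
- A reader might infer that early switching is common in recurrent glioblastoma. The documents give no rate, and inclusion criterion 8 requires that no available therapy be likely to provide clinical benefit.

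**Conclusion.** The point holds in two parts. First, 8.8.1 and 9.4 conflict explicitly on SAE reporting for a participant who switches therapy with an unresolved toxicity, and 8.3.1 does not resolve it. Second, for anyone who switches within 30 days of the last dose, the TEAE window is longer than the routine SAE reporting period of 9.4, with no flag to show which events followed the switch.

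The effect is limited and cannot be quantified from the documents. It is confined to early switchers, whose share is not given, and to at most 30 days each. What may be lost under 9.4 is SAEs judged unrelated; for non-serious AEs the position after a switch is ambiguous. The worked dates are assumptions chosen to show how the rules diverge.

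Two further inferences should be resisted. The SAP does not depart from the Protocol, because 10.4.3 has the same 30-day definition; the mismatch is between collection and analysis. And a safety visit 38 days after the last dose does not in itself lose data. The anchor needs reconciling because the documents give different ones, and because the 28-day minimum in 4.2 could close the visit before the TEAE window ends.

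**What to change.** - **Protocol 7.1.2, 8.3.1, 8.8.1 and 9.4:** state one AE and SAE collection window, matching the 30-day TEAE window, and say explicitly what happens when new anticancer therapy starts. Separate collection of new events from follow-up of events already recorded, so that the resolution limit applies only to the latter. Check Section 6.6 at the same time, since concomitant-medication recording there also stops at new therapy.
- **SAP:** flag TEAEs with onset on or after the start of new anticancer therapy, and show the key TEAE tables with and without them. The dates should be available: Protocol 8.8.2 captures new treatment for those who stop for reasons other than progression, 8.8.3 collects subsequent regimens during survival follow-up, and Listing 2.4.11 already covers post-treatment therapy.
- **Safety visit:** reconcile the anchor across Section 4.2, Table 2, Section 8.8.1 and Table 3 so that, absent a switch, the visit or contact is not before day 30 after the last dose and covers the whole TEAE window. Simply adopting 4.2 as written would not do this.

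The cost is wording changes in several protocol sections, one SAP flag, a few repeat tables and slightly more AE entry for participants who switch within 30 days.
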